10.1.1 Tumor Evaluation

Modified RECIST 1.1 criteria will be used to assess patient response to treatment by determining PFS and ORR. The modified RECIST 1.1 guidelines for measurable, non-measurable, target and non-target lesions and the objective tumour response criteria (complete response, partial response, stable disease or progression of disease).

The methods of assessment of tumour burden used at baseline, CT or MRI scans of chest, abdomen and pelvis must be used at each subsequent follow-up assessment.

Following the baseline assessment, efficacy for all patients will be assessed by objective tumour assessments every 6 weeks relative to date of first dose until objective disease progression as defined by modified RECIST 1.1. See Study Schedule (Table 1) for further details.

[Type here]

[Type here]

[Type here]

Pembrolizumab + Ramucirumab (Ver 2.5, Oct 2024)

If a patient discontinues treatment (and/or receives a subsequent cancer therapy) prior to progression then the patient should still continue to be followed until objective disease progression as defined by modified RECIST 1.1.

Categorisation of objective tumour response assessment will be based on the modified RECIST 1.1 criteria of response: CR (complete response), PR (partial response), SD (stable disease) and PD (progression of disease). Target lesion (TL) progression will be calculated in comparison to when the tumour burden was at a minimum (i.e. smallest sum of diameters previously recorded on study). In the absence of progression, tumour response (CR, PR, SD) will be calculated in comparison to the baseline tumour measurements obtained before starting treatment.

For patients with non-measurable disease only at baseline, categorisation of objective tumor response assessment will be based on the modified RECIST 1.1 criteria of response: CR, PD and Non CR/Non PD.

If the investigator is in doubt as to whether progression has occurred, particularly with response to NTL (non-target lesion) or the appearance of a new lesion, it is advisable to continue treatment until the next scheduled assessment or sooner if clinically indicated and reassess the patient's status. If repeat scans confirm progression, then the date of the initial scan should be declared as the date of progression.

Any other sites at which new disease is suspected should also be appropriately imaged. If an unscheduled assessment was performed and the patient has not progressed, every attempt should be made to perform the subsequent assessments at their scheduled visits.

To achieve 'unequivocal progression' on the basis of non-target disease, there must be an overall level of substantial worsening in non-target disease such that, even in presence of SD or PR in target disease, the overall tumour burden has increased sufficiently to merit discontinuation of therapy. A modest 'increase' in the size of one or more non-target lesions is usually not sufficient to qualify for unequivocal progression status.

Following progression, patients should continue to be followed up for survival weeks as outlined in the Study Schedule (see Appendix 1).

It is important to follow the assessment schedule as closely as possible.

10.2 Safety assessments

10.2.1 SAFETY EVALUATIONS

Treating physicians are responsible for monitoring the safety of patients who have entered this study and for alerting Lilly & Merck its designee to any event that seems unusual, even if this event may be considered an unanticipated benefit to the patient.

The treating physician is responsible for the appropriate medical care of patients while on this study.

[Type here]

[Type here]

[Type here]

The treating physician remains responsible for following, through an appropriate health care option, AEs that are serious, considered related to care received while on this study, or that caused the patient to discontinue from the study. The patient should be followed until the event is resolved or explained. The frequency of follow-up evaluation is left to the discretion of the patient's physician.

10.2.2 Adverse Events

Lack of drug effect is not an AE in this study.

Cases of pregnancy that occur during maternal or paternal exposures to ramucirumab/pembrolizumab should be reported. Data on fetal outcome and breastfeeding are collected for regulatory reporting and drug safety evaluation.

Site personnel will record in the patient's medical record the occurrence and nature of each patient's preexisting conditions, including clinically significant signs and symptoms of the disease under treatment.

After the ICF is signed, site personnel will record the occurrence and nature of any AEs targeted for collection in this study. Information on the AEs collected during the patient's time on the Study will be reported to Lilly & Merck or its designee at the time the patient discontinues ramucirumab and pembrolizumab. Adverse events must also be documented at the time of discontinuation and for 30 days after last dose of protocol therapy.

The treating physician will decide whether he or she interprets the recorded AEs as related to disease, study medication, study procedure, or other concomitant treatment or pathologies. To assess the relationship of the AE to the study drug or procedure, the following terminologies are defined:

- **Probably related:** A direct cause and effect relationship between the study treatment and the AE is likely.
- **Possibly related:** A cause and effect relationship between the study treatment and the AE has not been demonstrated at this time and is not probable, but is also not impossible.
- **Does not know:** The treating physician cannot determine.
- **Not related:** Without question, the AE is definitely not associated with the study treatment.

The treating physician should classify all "probably related," "possibly related," or "does not know" AEs and SAEs as related to study drug/study procedure.

Patients will be evaluated for AEs at each visit and will be instructed to call their physician to report any AEs between visits.

[Type here]

[Type here]

[Type here]

The NCI-CTCAE (v5.0) will serve as the reference document for choosing appropriate terminology for, and grading the severity of, all AEs and other symptoms. For AEs without matching terminology within the NCI-CTCAE (v5.0) criteria, the treating physician will be responsible for selecting the appropriate system organ class and assessing severity grade based on the intensity of the event.

Apart from SAEs and AESIs, only those AEs Grade 3 or worse will be reported at the time the patient discontinues ramucirumab/pembrolizumab therapy.

10.2.3 Serious Adverse Events

A serious adverse event is any AE from this study that results in one of the following outcomes:

- death
- a life-threatening experience (that is, immediate risk of dying)
- persistent or significant disability/incapacity
- initial or prolonged inpatient hospitalization
- congenital anomaly/birth defect
- considered significant by the investigator for any other reason

Important medical events that may not result in death, be life-threatening, or require hospitalization may be considered SAEs when, based upon appropriate medical judgment, they may jeopardize the patient and may require medical or surgical intervention to prevent one of the outcomes listed in this definition.

Serious adverse event collection begins after the patient has signed informed consent and has received ramucirumab. If a patient experiences an SAE after signing informed consent, but prior to receiving ramucirumab, the event will not be reported as an SAE unless the investigator feels the event may have been caused by a protocol required procedure. Serious adverse events must also be documented at the time of discontinuation and for 30 days after last dose of protocol therapy. Serious adverse events that occur more than 30 days after last dose of protocol therapy must be reported if deemed related to protocol procedures or study drug by the patient's physician.

Study personnel must report SAE to IRB according to the institutional regulation. Lilly adheres to procedures for SUSAR records and expedited reporting consistent with worldwide regulations and relevant detailed guidelines. SAE reporting to Merck Global Safety (to: Worldwide Product Safety, [contact]) should be reported within 2 business days but no longer than 3 calendar days of learning of event.

Planned surgeries should not be reported as SAEs unless the underlying medical condition has
[Type here] [Type here] [Type here]

Pembrolizumab + Ramucirumab (Ver 2.5, Oct 2024)

worsened after commencing ramucirumab & pembrolizumab therapy.

Planned hospitalizations or procedures for preexisting conditions that are already recorded in the patient's medical history at the time of study enrollment should not be considered SAEs. Hospitalization or prolongation of hospitalization without a precipitating clinical AE (for example, for the administration of study therapy or other protocol-required procedure) should not be considered SAEs.

Death due to disease progression should not be reported as an SAE unless the treating physician also deems there to be a contribution possibly related to the study drug.

If a treating physician becomes aware of an SAE occurring after the patient's participation in the study has ended, and the treating physician believes that the SAE is related to ramucirumab and pembrolizumab, the treating physician should report the SAE to the Lilly and Merck, and the SAE will be entered in the pharmacovigilance system.

All SAEs identified while a patient is on this study will be reported to Lilly and Merck as noted above.

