--	--

[Type here]

[Type here]

[Type here]

Pembrolizumab + Ramucirumab (Ver 2.5, Oct 2024)

	
is detected). Chronic HBV infection with anti-viral agent prophylaxis is allowed.
 
22. Has known liver cirrhosis at a level of Child-Pugh B (or worse) or cirrhosis (any degree) and a history of hepatic encephalopathy or clinically meaningful ascites resulting from cirrhosis. Clinically meaningful ascites is defined as ascites from cirrhosis requiring diuretics or paracentesis.
 
23. The patient is pregnant or breastfeeding

Goal:	To estimate efficacy and safety of combination therapy of Ramucirumab and Pembrolizumab in patients with metastatic gastric or GEJ adenocarcinoma
Planned Sample Size:	
: A maximum of 26 patients (considering 5% drop out rate) will be recruited to this single-arm phase II trial.
 
In this single-arm phase II trial, 25 people were calculated using Simon's two-stage design and a total of 26 patients will be recruited to account for a 5% dropout rate. The sample size is calculated by use of a two-stage minimax Simon's design to control the type I error at 5 % for null hypothesis that, for arm, the true response was 15 % or below and to have 85 % of power if the true response was 40 % or higher. 15 evaluable patients are to be treated in the first stage. If 1 or fewer response are observed in the first stage, the arm will be stopped. If at least 2 responses are observed in the first stage, 10 additional evaluable patients are to be entered onto the second stage. At the final analysis, the null hypothesis will be rejected if at least 7 responses are observed in 25 evaluable patients. RR is reported with its exact 95% CI.

Duration of Study:	Until 100% enrollment from approval regulatory authority
Study design (Dosage & Treatment):	
Patients will continue to receive study treatment, until they demonstrate objective disease progression (determined by modified RECIST 1.1) or until they meet any other discontinuation criteria.
 
 - Ramucirumab 8mg/kg on q2W - Pembrolizumab 200mg on q3W (pembrolizumab first followed by ramucirumab when concurrently administered on the same day)

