	

The diagram illustrates the study timeline. It begins with a 'Screening' phase, followed by 'Cycle 1 (42 days)'. A 'Baseline Fresh Tissue Biopsy' is performed at the start of Cycle 1. Treatment days are marked as D1, D8, D15, D22, D29, and D36. Ramucirumab (R) is administered on D1, D15, and D29. Pembrolizumab (P) is administered on D1 and D22. A legend specifies: R: Ramu : 8mg/kg on D1, D15, D29 (every two weeks); P: Pembro : 200mg on D1, D22 (every three weeks).

 

If ramucirumab had to be stopped due to intolerable toxicity, pembrolizumab will be continued until unacceptable toxicity, disease progression or upto 35 cycles.

Specimen for biomarker and Genetic analysis	
1. Tumor Biopsy Tumor biopsies will be obtained from all subjects in the study. However, tumor biopsy can be exempted in cases considered as not safe or not accessible. It may be performed twice as below if possible.
 
1) Pre-treatment : Obtained at screening (Day 28) from the primary site.2) If disease progresses, optional tumor biopsy may be obtained after it is confirmed. 
2. Blood Collection For analysis of biomarker(ct DNA), peripheral blood of 10 ml will be collected from all patients at every cycle D1 and at confirmed disease progression.

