8.1.2 Pembrolizumab

Pembrolizumab 200 mg will be administered as a 30 minute IV infusion every 3 weeks. Sites
[Type here] [Type here] [Type here]

Pembrolizumab + Ramucirumab (Ver 2.5, Oct 2024)

should make every effort to target infusion timing to be as close to 30 minutes as possible.

However, given the variability of infusion pumps from site to site, a window of -5 minutes and +10 minutes is permitted (i.e., infusion time is 30 minutes: -5 min/+10 min).

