10.2.5 Adverse Events of Special Interest (AESIs)

Adverse events of special interest, which may or may not be associated with ramucirumab therapy, include infusion-related reactions, hypertension, arterial or venous thrombotic events, bleeding (hemorrhagic) events, proteinuria, gastrointestinal perforation, reversible posterior leukoencephalopathy syndrome (RPLS), congestive heart failure (CHF), impaired wound healing, and liver failure and other significant liver injury. The worst grade of each of these events, if they occurred, will be reported on the designated CRF at the time the patient discontinues ramucirumab therapy.

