Grades 3 or 4 Grade 3: Prolonged (i.e., not rapidly responsive to symptomatic medication and/or	Stop Infusion. Additional appropriate medical therapy may include but is not limited to: IV fluids Antihistamines NSAIDS	No subsequent dosing

[Type here]

[Type here]

[Type here]

Pembrolizumab + Ramucirumab (Ver 2.5, Oct 2024)

NCI CTCAE Grade	Treatment	Premedication at subsequent dosing
brief interruption of infusion); recurrence of symptoms following initial improvement; hospitalization indicated for other clinical sequelae (e.g., renal impairment, pulmonary infiltrates) Grade 4: Life-threatening; pressor or ventilatory support indicated	Acetaminophen Narcotics Oxygen Pressors Corticosteroids Epinephrine Increase monitoring of vital signs as medically indicated until the subject is deemed medically stable in the opinion of the investigator. Hospitalization may be indicated. Subject is permanently discontinued from further trial treatment administration.	
Appropriate resuscitation equipment should be available in the room and a physician readily available during the period of drug administration.		

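### SAE collection opens only after ramucirumab, although pembrolizumab is infused first on day 1; the AESI list also names no immune-mediated events as such

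*Combined protocol and SAP*

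**What the plan says.** **Start of SAE collection.** Section 10.2.3 states: "Serious adverse event collection begins after the patient has signed informed consent and has received ramucirumab". For an SAE after consent but before ramucirumab, it adds that "the event will not be reported as an SAE unless the investigator feels the event may have been caused by a protocol required procedure". The same section sets the Merck reporting deadline at 2 business days and no more than 3 calendar days.

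**Order of infusion.** The Synopsis, repeated in Section 7.1, specifies "pembrolizumab first followed by ramucirumab when concurrently administered on the same day". The cycle diagram in the Synopsis and the schedule in Appendix 1 place both drugs on cycle 1 day 1.

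**Special-interest events.** Section 10.2.5 opens with "Adverse events of special interest, which may or may not be associated with ramucirumab therapy" and lists infusion-related reactions, hypertension, thrombotic events, bleeding, proteinuria, GI perforation, RPLS, heart failure, impaired wound healing and significant liver injury. The worst grade of each is reported when ramucirumab is discontinued. For the remainder, Section 10.2.2 says: "Apart from SAEs and AESIs, only those AEs Grade 3 or worse will be reported", again at discontinuation.

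**The concern.** The trial's stated goal covers the safety of the combination, but the SAE start is defined by ramucirumab alone. A patient treated on schedule has therefore already been exposed to pembrolizumab when SAE collection opens. A serious reaction to that infusion, before ramucirumab, is denied SAE status by a written rule and falls outside the expedited Merck report.

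The AESI list has a related imbalance. Section 8.4.1 says pembrolizumab events may be immunologic in origin and gives hold and discontinuation rules for them, while Section 10.2.5 is built around ramucirumab. Section 13.2 makes safety wholly descriptive, so the safety result is only as good as the capture of events.

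**Working it through.** The plan gives no statistical figure to reproduce. The check sets the rules side by side, with some arithmetic on timing.

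**1. Is there always a gap on day 1?** Both drugs are due on day 1 and pembrolizumab goes first. If the order is followed, exposure to a study drug precedes the start of SAE collection in every patient.

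**2. How long is it?**
- Section 8.1.2 gives "infusion time is 30 minutes: -5 min/+10 min". That is 30 − 5 = 25 minutes to 30 + 10 = 40 minutes, plus any interval before ramucirumab is given.
- If ramucirumab cannot be given within 3 days of its scheduled date, Section 8.4.1 moves it to the next scheduled time point after the event resolves. From day 1 that is day 15 at the earliest: 15 − 1 = 14 days, or 11 to 17 days with the 3-day visit window.
- For a Grade 3 or 4 pembrolizumab infusion reaction, the table in Section 10.2.6 says: "Subject is permanently discontinued from further trial treatment administration". If this happens before ramucirumab, the start condition is never met.

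**3. Does the procedure exception close the gap?** Not clearly. Later in Section 10.2.3, protocol procedures and study drug are named as separate possible causes, so a drug reaction is not obviously a procedure event. The closing sentence on reporting all on-study SAEs refers back to the rules above it and does not override them.

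**4. What is still recorded?**

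| Route | Covers the event in the gap? |
|---|---|
| Section 7.2, AEs captured from consent | Yes, as an AE |
| Section 10.2.5, infusion reactions as AESIs | Yes, if it is an infusion reaction |
| Section 10.2.2, Grade 3 or worse | Yes, at discontinuation |
| Section 10.2.3, SAE status and Merck timeline | No, under the start rule |
| Sections 7.5 and 10.2.3, 30 days after last dose | SAEs in that period are covered, without any condition of prior ramucirumab |

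The last two rows conflict for a patient who stops after pembrolizumab alone.

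**5. Immune-mediated events.** Five rows of the Section 8.4.1 table require a pembrolizumab hold at Grade 2: diarrhea/colitis, AST/ALT/bilirubin increase, hypophysitis, pneumonitis, and renal failure or nephritis. The liver row may overlap the AESI category of significant liver injury. The other 5 − 1 = 4 are not named in Section 10.2.5. If non-serious, they also fall below the Grade 3 floor in Section 10.2.2.

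In addition, AESI reporting is tied to stopping ramucirumab. The Synopsis lets pembrolizumab continue alone for up to 35 cycles when ramucirumab is stopped for toxicity, whereas Section 7.1 stops both drugs together. Those two passages contradict each other and must be reconciled.

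**The case against.** The strongest reply is that little is lost.

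- **The gap is short.** When day 1 runs to plan it lasts under an hour plus any interval before ramucirumab. A pembrolizumab event that arises after ramucirumab is inside SAE collection. This stands.
- **The event is counted.** A severe infusion reaction is an AE, an AESI and a Grade 3 or worse event. This stands. What is lost is SAE status and the expedited timeline.
- **The Grade 3 floor may not limit collection.** Section 10.2.2 describes AE information sent to the two drug suppliers, so the floor may govern only that transfer. AEs are asked about at every visit, and Section 13.2 sets no grade limit. This is a fair reading, but Section 10.2.2 also speaks of AEs targeted for collection, so the text leaves it open.
- **Other routes exist for immune events.** An investigator may classify a significant Grade 2 event as serious. Section 8.4.1 also points to an external guidance document on events of clinical interest, whose reporting duties cannot be checked here. Both points stand, but neither is a stated reporting rule for these events.

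A reader might infer something stronger: that for a patient stopped after a day 1 pembrolizumab reaction, SAE collection never opens, even for later immune-mediated events. The documents do not support this. Section 10.2.3 also requires SAEs to be documented at discontinuation and for 30 days after the last dose, and drug-related SAEs after that. Section 7.5 captures all AEs and SAEs in the 30-day period. None of these sentences requires prior ramucirumab.

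Nor should one weigh the gap as 1/26 = 3.8 percentage points of incidence. The severe infusion reaction that best illustrates the problem is still in the AE counts.

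**Conclusion.** The point holds in a limited form. Followed as written, the start rule denies SAE status and the 2-business-day, 3-calendar-day Merck report to a serious event arising after pembrolizumab starts and before ramucirumab is received. The window is at least 25 to 40 minutes, and about 14 days or more if the day 1 ramucirumab dose is missed. Such events are probably rare; the documents give no rate, so no expected number can be stated. The conclusion assumes that an infusion is not itself a protocol required procedure. The rule also conflicts with the follow-up provisions in Sections 7.5 and 10.2.3.

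The AESI part is secondary and less certain: non-serious Grade 2 immune-mediated events that trigger a hold may not be reported, depending on how the Grade 3 floor is read. Both parts concern the completeness of descriptive safety data. The ORR test and the Simon design are not affected.

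**What to change.** 1. In Section 10.2.3, replace both references to receipt of ramucirumab with the first dose of any study drug (pembrolizumab or ramucirumab). Reconcile this with the 30-day follow-up in Section 7.5 and with the later sentences of Section 10.2.3 on all on-study and post-study SAEs.
2. In Section 10.2.5, add the immune-mediated events of the Section 8.4.1 table. Record them until both drugs are stopped, plus the safety follow-up period. Ending capture when either drug stops would be too early, because pembrolizumab may continue alone under the Synopsis and Section 8.4.1 says its events can appear several months after the last dose.
3. In Section 10.2.2, state whether the Grade 3 floor applies to the CRF or only to the transfer to the drug suppliers.
4. In Section 13.2, add a table of these events.

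The cost is a change of wording and a few CRF lines. AEs are already assessed at every visit, so no new visit or procedure is needed.
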